3.2 Exclusion Criteria

- 3.2.1 Patients must not have any significant infections or medical illnesses that in the investigator's opinion cannot be adequately controlled with appropriate therapy or would compromise the patient's ability to tolerate NU-0129.
- 3.2.2 Patients must not have a history of any other cancer unless they are in complete remission and off of all therapy for that disease for a minimum of 3 years.

NOTE: Non-melanoma skin cancer or carcinoma in-situ of the cervix are exceptions and may be permitted after discussion with study QAM.

- 3.2.3 Patients must not have had radiation therapy \leq 12 weeks prior to starting study treatment.

3.2.4 Patients must not have had prior cancer therapy (including biologic, cytotoxic, and experimental therapies, nitrosoureas, and Gliadel wafers or other surgically implantable antitumor treatment) within 21 days of registration. If questions arise, please contact the PI.

NOTE: Patients must not have had Novocure within 24 hours of registration

3.2.5 Hormonal tumor therapies should not be administered within 14 days of registration. Exceptions may be discussed with the PI.

3.2.6 Patients must not have symptomatic hypertension.

3.2.7 Patients with known human immunodeficiency virus (HIV) infection or chronic or acute Hepatitis B or C are not eligible.
Note: Patients do not need to have HIV, Hepatitis B, or Hepatitis C testing at screening.

3.2.8 Female patients who are pregnant or breast feeding are not eligible.

3.2.9 Patients are not eligible if they are unwilling or unable to comply with the protocol.

4.0 TREATMENT PLAN

4.1 Overview

The phase 0 trial will evaluate the safety, pharmacokinetics, and bio-distribution of a systemically (IV) administered SNA gold nanoparticle, NU-0129. Once registered, eligible patients will receive intravenous NU-0129 one time as an inpatient followed by tumor resection within 8-48 hours post-infusion. Patients will be monitored with telemetry, vital signs and labs before and after the infusion as indicated in section 5.0. Bio-distribution will be analyzed with PK blood draws over 24 hours and collection of tissue during the scheduled surgery.

4.2 NU-0129 Administration

Patients will be admitted for a one-time administration of IV NU-0129 at a nominal dose of 0.04mg/kg (approximately 0.03 to 0.05mg/kg), based on the patient's weight at screening. Patients will be dosed based on total body weight and the resulting dose will be rounded to one of the 5 dose groups as shown in dosing chart below.

Patient's weight in kg	Dose in mg (Oligonucleotide component)	Corresponding dose (mg/kg)
Up to 37.0 kg	0.987 mg	Up to 0.027
≥ 37.0 to < 61.7 kg	1.974 mg	0.053 to 0.032
≥ 61.7 to < 86.4 kg	2.96 mg	0.048 to 0.034
≥ 86.4 to < 111.0 kg	3.95 mg	0.046 to 0.036
≥ 111.0 to 135.7 kg	4.94 mg	0.045 to 0.036

The infusion rate will be 5.0-8.0 mL/minute over approximately 20 - 50 minutes. The flow rate will be monitored closely and the tissue surrounding the catheter examined frequently for any signs of extravasation. Patients will be monitored with telemetry from the beginning of the infusion for at least 8 hours post-infusion. Thereafter, vitals will be monitored at least every 4 hours for a total of 24 hours from the end of infusion.

Immediately after the infusion is completed, PK blood draws will take place at 1, 3, 5, 10, 30, and 60 minutes (± 1 minute) post-dose as well as 4, 8 and 24 hours (± 5 minutes)

post-dose. If necessary, blood draws may take place during the patient's resection surgery, however this should be avoided when possible.

Patients will remain inpatient for a tumor resection, occurring 8-48 hours after treatment with NU-0129. Vitals will be measured continuously throughout the surgery. Standard of care post-operative procedures will take place per institutional guidelines, including a brain MRI within 48 hours after the resection. Physician determined response will be determined using RANO (Response assessment in neurology-oncology) criteria. (NOTE: patient response is not expected based on a single sub-therapeutic dosing. In addition, the surgery may confound response assessment.)

4.3 Toxicity Management & Dose Delays/Modifications

Each patient will be assessed for the development of toxicity from the time of consent to 21 days post-dose. Toxicity will be assessed according to CTCAE v4.03. Any patient who receives at least one dose of study therapy will be evaluable for toxicity endpoints.

Patients should be closely observed for infusion-related reactions and any other form of toxicity. Treatment for infusion reactions, and all events, will be based on institutional guidelines. Grading and resolution of the event will be reported using CTCAE v4.03. For example, if a severe infusion reaction occurs, the infusion rate should be cut in half to 2.0-5.0mL/minute.

During the surgical resection, the resected tumor sample should be observed for potential discoloration. The locations and degree of discoloration must be carefully recorded and assessed for relationship to treatment with NU-0129.

There will be no dose delays or modifications as this is a single-dose therapy. However, each patient will be closely monitored for toxicities during the first 21 days after receiving study treatment. Any adverse event that is reported as a Grade 2 toxicity or higher, that is at least possibly related to NU-0129, will be referred to the external DSMB (Data Safety Monitoring Board) for review. The DSMB will review the event within 24 hours of notification to determine a plan for dosing future patients and immediate action if necessary. In addition, each patient's safety data will be reviewed at the end of the 21-day period post therapy and the DSMB will provide a recommendation for future dosing. No additional patients will be registered until the DSMB provides their analysis.

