8.1.5 Protocol dose specifics

Each patient's dose will be based on his or her weight at screening. Patients will be dosed based on total body weight and the resulting dose will be rounded to one of the 5 dose groups as shown in dosing chart below. Nominal dose will be 0.04mg/kg (approximately 0.03 to 0.05 mg/kg).

Patient's weight in kg	Dose in mg (Oligonucleotide component)	Corresponding dose (mg/kg)
Up to 37.0 kg	0.987 mg	Up to 0.027
≥ 37.0 to < 61.7 kg	1.974 mg	0.053 to 0.032

≥ 61.7 to < 86.4 kg	2.96 mg	0.048 to 0.034
≥ 86.4 to < 111.0 kg	3.95 mg	0.046 to 0.036
≥ 111.0 to 135.7 kg	4.94 mg	0.045 to 0.036

8.1.6 Preparation. Refer to pharmacy manual for complete study drug preparation procedures.

- Prior to reconstitution, the vials should be equilibrated to room temperature to reach room temperature for 5-30 minutes. .
- Vials can be stored at room temperature (20-25 °C) for up to 3 hours. This includes thawing time and reconstitution time.
- Vials should not be refrozen after thawing.
- Each NU-0129 manufactured clinical vial should be reconstituted in 1mL SWFI for final concentration approximately 0.987 mg/ml.
- Mix the solution in the vial by gentle swirling or gentle shaking by benchtop sonicator, if available.
- Visually inspect for particulate matter and discoloration prior to administration. Reconstituted solution should red or maroon color, free of visible particles.
- Calculate the dose and the amount of vials required based on the dosing chart.
- Withdraw the full content of the NU-0129 vials and inject into an appropriate size bag of normal saline (0.9% sodium chloride).
- Reconstituted solution should be further diluted with normal saline (0.9% sodium chloride) to 1:50 dilution.
- Preparation should take place immediately prior to administration, but, if needed, reconstituted vials and/or IV bags may be stored at room temperature (20-25 °C) for up to 8 hours (including administration time).
- Administer study drug using non-PVC/DEHP administration set with a sterile, non-pyrogenic, low-protein binding 0.22 µm filter.
- Visually inspect final product for particulate matter and discoloration prior to administration. Do not use and discard the drug product vial if extraneous particulate matter is observed.

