8.1.10 Side effects

As this is a first-in-human trial, side effects in this population are not completely known. In the primate and non-primate treatment trials, a few noted side effects were observed. Gold nanoparticle accumulation in the liver has occurred in some pre-clinical studies as well as skin discoloration following the infusion have been seen with animal models displaying a purple hue to their baseline skin

tone. Hypercholesterolemia was also observed in the non-primate model (rat model).

Possible side effects:

Liver Damage
Skin Discoloration
Infusion Reaction
Hypercholesterolemia
Low blood pressure

There is no significant toxicity associated with the chemistry or manufacturing of the drug product.

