8.1.11 Nursing implications

The dose (based on dosing chart) will be based on the patient's weight at baseline. The infusion rate will be 5.0-8.0 mL/minute. A sterile, non-pyrogenic, low-protein binding 0.22 μ m in-line filter must be used during administration to remove any adventitious particles. If the infusion set does not contain in-line filter, 0.22 μ m add-on filter should be used. The flow rate will be monitored closely and the tissue surrounding the catheter examined frequently for any signs of extravasation.

Drug Administration Log should be completed by administering nurse and returned to study coordinator, documenting date and time of infusion start/ stop, interruptions (if any). Any staining or discoloration of the syringe, IV bag, delivery device, and /or administration set should be documented in the Administration Log.

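### The halved infusion rate in section 4.3 (2.0-5.0 mL/minute) is not half of the 5.0-8.0 mL/minute starting rate; half is 2.5-4.0 mL/minute

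*Combined protocol and SAP*

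**What the plan says.** Section 4.2 (NU-0129 Administration) sets the planned rate: "The infusion rate will be 5.0-8.0 mL/minute over approximately 20 - 50 minutes". Section 8.1.11 (Nursing implications) repeats it: "The infusion rate will be 5.0-8.0 mL/minute". No other starting rate appears in the document.

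Section 4.3 (Toxicity Management & Dose Delays/Modifications) first gives the general rule, "Treatment for infusion reactions, and all events, will be based on institutional guidelines". It then offers an example: "if a severe infusion reaction occurs, the infusion rate should be cut in half to 2.0-5.0mL/minute".

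Section 8.1.10 lists "Infusion Reaction" among the possible side effects. The nursing section gives the starting rate but no reduced rate. The summary of changes in Appendix B records edits to the toxicity-management section in Amendments 2 and 3, but no entry concerns the infusion rate.

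**The concern.** The sentence in section 4.3 contains an instruction (halve the rate) and a result (2.0-5.0 mL/minute), and the result does not follow from the starting rate given elsewhere. The upper limit is the more awkward end because 5.0 mL/minute is itself a permitted starting rate. Someone who reads the numbers and not the words could take 5.0 mL/minute as an acceptable reduced rate, although for a patient started at 5.0 it is no reduction.

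At stake is the clarity of a safety instruction that would be consulted during a severe reaction, in a study where human side effects are not yet fully known. Within this protocol, section 4.3 is the only place that gives a numeric reduced rate. The institutional guidelines and the separate pharmacy manual are not available here, so whether either gives another rate cannot be checked.

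**Working it through.** **Inputs**

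- Starting rate: 5.0-8.0 mL/minute (sections 4.2 and 8.1.11).
- Printed reduced rate: 2.0-5.0 mL/minute, described as half (section 4.3).
- Stated infusion time: approximately 20-50 minutes (section 4.2).
- Vial content about 0.987 mg, reconstituted in 1 mL (section 8.1.6), with the dilution instruction "Reconstituted solution should be further diluted with normal saline (0.9% sodium chloride) to 1:50 dilution" in the same preparation list.
- Dosing chart: 0.987, 1.974, 2.96, 3.95 and 4.94 mg (sections 4.2 and 8.1.5), which are 1 to 5 vials.

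**1. Attempt to reproduce the printed range**

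Reduced rate = starting rate / 2.

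| Starting rate (mL/minute) | Half (mL/minute) |
|---|---|
| 5.0 | 2.5 |
| 6.0 | 3.0 |
| 7.0 | 3.5 |
| 8.0 | 4.0 |

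The result is 2.5-4.0, so the printed 2.0-5.0 is not reproduced.

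**2. Size of the discrepancy**

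- Lower limit: 2.0/2.5 = 0.80, which is 20% too low.
- Upper limit: 5.0/4.0 = 1.25, which is 25% too high.

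**3. Could the printed range come from something else?**

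- Back-calculation: 2 x 2.0 = 4.0 and 2 x 5.0 = 10.0. A starting range of 4.0-10.0 mL/minute would be needed, and the protocol contains none.
- Rounding: taking 2.5-4.0 outward to whole numbers gives 2-4. That could explain 2.0 but not 5.0.

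**4. Is the starting rate the figure that is wrong?**

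Read the dilution as about 50 mL of infusate per 1 mL vial (an assumption about what 1:50 means). Two to five vials, which are chart rows 2 to 5, then need 100-250 mL.

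- At 5.0 mL/minute: 100/5.0 = 20 minutes and 250/5.0 = 50 minutes. This is the stated duration.
- At 8.0 mL/minute: 100/8.0 = 12.5 minutes and 250/8.0 = 31.25 minutes.
- If 1:50 means 1 mL added to 50 mL, the volumes are 102-255 mL and the times at 5.0 mL/minute are 20.4-51 minutes, so the conclusion is the same.
- Row 1 (one vial, 50 mL) would take 10 minutes at 5.0 mL/minute and falls outside the stated duration on either reading.

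The lower end of the starting rate therefore fits the volumes and the stated time, and the full range is given identically in two sections. The fault lies in section 4.3.

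**5. What the printed limits would mean if read alone**

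| Starting rate (mL/minute) | Reduction if set to 5.0 | Reduction if set to 2.0 |
|---|---|---|
| 5.0 | 1 - 5.0/5.0 = 0% | 1 - 2.0/5.0 = 60% |
| 8.0 | 1 - 5.0/8.0 = 37.5% | 1 - 2.0/8.0 = 75% |

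A halving is a 50% reduction. The printed limits run from no reduction to a 75% reduction.

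**The case against.** The strongest reply is that the operative words are the instruction to halve, and they work. Every permitted rate, once halved, falls between 2.5 and 4.0 mL/minute, inside the printed range. Anyone who follows the words reaches a correct rate and meets no conflict. Leaving a patient at 5.0 mL/minute would itself breach the instruction to halve, so the sentence does not permit continuing unchanged. The lower limit errs toward a slower infusion and may be rounding. The percentages above compare printed limits; they are not errors in a rate that a patient would receive if the instruction were followed.

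The context also limits the consequences. The sentence is an example under a rule that defers to institutional guidelines. Section 4.2 requires close monitoring of the flow rate and telemetry from the start of the infusion. Section 4.3 sends any event of Grade 2 or higher that is at least possibly related to the drug to the external DSMB, which reviews it within 24 hours of notification.

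All of this stands as a limit on the weight of the point. It does not make the printed range correct, and it leaves 5.0 mL/minute unexplained. DSMB review comes after the event, so it does not help the person adjusting the infusion.

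**Conclusion.** The point holds. The printed range does not match half of the only starting rate in the protocol: 2.0-5.0 is written where 2.5-4.0 mL/minute is correct, 20% low at one end and 25% high at the other. The upper limit coincides with the lowest permitted starting rate. The conclusion rests on the two matching statements of the starting rate and on simple division; the volume check depends on the reading of the dilution but only confirms where the fault lies.

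The practical weight is small, and no endpoint, sample size or analysis is affected. It should still be corrected, because it is a wrong number in a first-in-human safety instruction and removing the contradiction costs almost nothing.

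**What to change.** In section 4.3, replace the range with wording such as: half the rate at which the reaction occurred (2.5-4.0 mL/minute for a starting rate of 5.0-8.0 mL/minute). Alternatively, delete the numbers and keep the instruction to halve. Repeating the reduced rate in section 8.1.11 would put it beside the starting rate for nursing staff. The cost is a few words in an amendment, with no new data, patients or procedures.

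The same amendment could tidy row 1 of the dosing chart (sections 4.2 and 8.1.5). This is a separate, optional matter, and the finding above does not depend on it.

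- **Weight limit.** A weight of exactly 37.0 kg falls in both row 1 (0.987 mg) and row 2 (1.974 mg), a twofold difference. Rounding to the nearest dose barely separates them: 0.04 x 37.0 = 1.480 mg, against a midpoint of (0.987 + 1.974)/2 = 1.4805 mg. Row 2 explicitly includes 37.0 kg, and its printed 0.053 mg/kg matches 1.974/37.0 = 0.0534. Limiting row 1 to weights below 37.0 kg is therefore the simplest repair, once the sponsor confirms that intent.
- **Dose label.** The mg/kg label for row 1 is reversed. Since 0.987/37.0 = 0.0267 and 0.987/30 = 0.0329, about 0.027 is the lowest value in that row, not the highest.

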4.4 Concomitant Medications/Treatments

All concomitant therapies must be recorded in the appropriate eCRF and source documents throughout the study, beginning with the time of written informed consent up to 21 days after NU-0129 administration.

4.4.1 Permitted Concomitant Medications

- Standard supportive care therapies needed for the management of symptoms are permitted, as clinically indicated.
- Hormonal birth control is permitted.

4.4.2 Prohibited Medications

The following medications are prohibited during the study:

- Any chemotherapy
- Anticancer immunotherapy
- Experimental therapy
- Radiation therapy

4.4.3 Adjuvant Treatment Post-Surgery

Patients often receive adjuvant treatment post resection as standard of care for GBM or GS. Patients should not receive such adjuvant treatment until at least 21 days after receiving NU-0129. After 21 days, patients may receive “physician’s best choice” treatment.

4.5 Other Modalities or Procedures

Tumor resection surgery is a standard of care procedure that will follow Northwestern Medicine institutional guidelines. The tissue collected during surgery will undergo testing for research purposes, however any other procedures related to surgery are standard of care.

4.6 Duration of Therapy

Within 14 days of study registration, patients will receive intravenous NU-0129 one time at nominal dose 0.04mg/kg. Patients will be admitted the morning of the planned NU-0129 infusion, and a tumor resection will occur 8-48 hours after administration. Patients will remain inpatient for standard of care post-operative procedures, including an MRI of the brain. Discharge will take place when clinically appropriate.

4.7 Duration of Follow Up

Patients will have a routine follow-up visit 7, 14, and 21 days after NU-0129 administration and then at least every 84 days (\pm 10 days) until disease progression or patient withdrawal for up to 2 years from treatment administration. They will be monitored for toxicities by physical exam and laboratory results as outlined in Table 5.0. They will also undergo a brain MRI at least every 84 days (\pm 10 days).

4.8 Removal of Subjects from Study Treatment and/or Study as a Whole

Patients can be taken off the study treatment and/or study as a whole at any time at their own request, or they may be withdrawn at the discretion of the investigator for safety, behavioral or administrative reasons. The reason(s) for discontinuation must be clearly documented on the appropriate eCRF and may include:

- Patient voluntarily withdraws from follow-up or prior to treatment
- Patient withdraws consent (no follow-up permitted)
- Patient is unable to comply with protocol requirements

4.9 Patient Replacement

If a patient withdraws for any reason after consent or registration but before receiving investigational product, he or she may be replaced.

If a patient receives study drug and does not have a post-treatment surgical resection, or the surgery is delayed beyond 48 hours of treatment for any reason, the patient will be evaluable for toxicity, but will be inevaluable for all other study endpoints; another patient may be added to accrual.

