2.2.3 Feasibility

- To assess the feasibility of giving NU-0129 as a standard treatment for recurrent GBM or GS.
- Feasibility will be calculated as the rate of successful production, delivery, and administration of the investigational product and subsequent resection.

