6.3 Secondary Endpoints

6.3.1 Pharmacokinetics

PK blood samples will be collected post-infusion at 1, 3, 5, 10, 30, and 60 minutes (+/- 1 minute), and 4, 8, and 24 hours (+/- 5 minutes).

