6.3.3 Feasibility

To assess feasibility, the rate of successful production, delivery, and administration of the investigational product and subsequent resection will be calculated.

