10.3.2 Secondary Objectives

To evaluate the bio-distribution of NU-0129 in tumor tissue we will provide descriptive statistics regarding intensity of concentration of particles in various parts of tumor tissue.

To evaluate the pharmacokinetics of NU-0129 in blood samples collected at 1, 3, 5, 10, 30, 60 minutes and 4, 8, and 24 hours post-dose, we will provide appropriate pharmacokinetic curves and parameters such as Cmax, Tmax etc.

To evaluate the feasibility of NU-0129 administration, we will record a) successes/failures, b) number of attempts to administrate nanoparticles.

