10.3.3 Exploratory Objectives

To evaluate the Bcl2L12 expression levels and apoptotic markers in the tumor tissue post-treatment, and to evaluate preliminary response (Overall Survival and Progression Free Survival at 2 years, as well as Overall Response Rate) we will describe expression levels and PFS and OS Kaplan-Meier curves corresponding to in study time up to 24 months.

In general, all patients properly included in the study who undergo surgery for tumor removed will be included in the analysis. Thus, an incorrect treatment schedule or drug administration would result in exclusion from the analysis of the tumor accumulation study. All conclusions will be based on all eligible patients. Subanalyses may then be performed on the basis of a subset of patients, excluding those for whom major protocol deviations have been identified. However, these subanalyses may not serve as the basis for drawing conclusions concerning treatment efficacy, and the reasons for excluding patients from the analysis should be clearly reported.

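### Section 4.9 takes dosed patients with no resection, or one after 48 h, out of the feasibility rate and the PK set, keeping them for toxicity only

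*Combined protocol and SAP*

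**What the plan says.** **Evaluability.** Section 4.9 covers a patient who received drug and then had no resection, or had it later than 48 h after treatment for whatever reason: "the patient will be evaluable for toxicity, but will be inevaluable for all other study endpoints; another patient may be added to accrual". Patients who leave before dosing may be replaced. Section 6.2 makes anyone given at least a partial dose evaluable for safety.

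**Feasibility (secondary).** Section 2.2.3: "Feasibility will be calculated as the rate of successful production, delivery, and administration of the investigational product and subsequent resection". Section 6.3.3 repeats it: "the rate of successful production, delivery, and administration of the investigational product and subsequent resection will be calculated". The analysis in section 10.3.2 is "we will record a) successes/failures, b) number of attempts to administrate nanoparticles". None of the three names a denominator or says how a resection outside the planned window is classed.

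**PK (secondary).** Section 6.3.1 schedules nine post-infusion samples, the last at 24 h with a 5-minute tolerance. Section 9.4.1 accepts draws taken during surgery.

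**Analysis population.** Section 10.3.3 and the Statistical Methodology row of the study summary say that "all patients properly included in the study who undergo surgery for tumor removed will be included in the analysis" and that "an incorrect treatment schedule or drug administration would result in exclusion from the analysis of the tumor accumulation study". Section 4.6 sets the timing: "a tumor resection will occur 8-48 hours after administration". Footnote 4 to Table 5.2 has OS and PFS analysed at 6 months in all patients.

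**The concern.** Under sections 2.2.3 and 6.3.3 a dosed patient who is never resected has not completed the feasibility sequence. Section 4.9 makes that patient inevaluable for feasibility, so the resection component cannot pull the rate down through absence, or through delay past 48 h. The reported rate would then not measure whether dosing followed by resection can be delivered.

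For PK, the exclusion is tied to an event that has nothing to do with blood sampling. A patient resected after 48 h can have all nine samples and still be dropped, while a patient sampled partly during surgery stays in. Section 10.2 chose 6 to 8 patients on practical grounds and adds, without figures, that the secondary outcomes can be estimated precisely enough. Each profile therefore counts.

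The statistical section also states populations that do not match section 4.9, so the analyst has no single rule to follow.

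**Working it through.** The plan states no feasibility target, precision or power, so there is no figure to reproduce. The check has four steps.

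**1. Feasibility rate under the two rules.** Let *n* be the number dosed (6 to 8, section 10.2) and *k* the number with absent resection, or late resection if that is counted as a failure. The documents do not give *k*; 1 and 2 are assumed, with every other step successful.

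- Section 4.9 as written: (*n* − *k*)/(*n* − *k*) = 100% for any *k*.
- All dosed: (*n* − *k*)/*n*.
- Exact (Clopper-Pearson) 95% limits for *x* successes in *n*: lower = 2.5% point of Beta(*x*, *n* − *x* + 1), upper = 97.5% point of Beta(*x* + 1, *n* − *x*).

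| Dosed | k | Section 4.9 (95% CI) | All dosed (95% CI) |
|---|---|---|---|
| 6 | 1 | 5/5 = 100% (47.8-100) | 5/6 = 83.3% (35.9-99.6) |
| 6 | 2 | 4/4 = 100% (39.8-100) | 4/6 = 66.7% (22.3-95.7) |
| 7 | 1 | 6/6 = 100% (54.1-100) | 6/7 = 85.7% (42.1-99.6) |
| 7 | 2 | 5/5 = 100% (47.8-100) | 5/7 = 71.4% (29.0-96.3) |
| 8 | 1 | 7/7 = 100% (59.0-100) | 7/8 = 87.5% (47.3-99.7) |
| 8 | 2 | 6/6 = 100% (54.1-100) | 6/8 = 75.0% (34.9-96.8) |

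If accrual is topped up to 8 evaluable patients, section 4.9 gives 8/8 (63.1-100%), against 8/9 = 88.9% (51.8-99.7%) or 8/10 = 80.0% (44.4-97.5%) among all dosed. If late resection is counted as a success, only absent resections produce a gap.

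**2. How likely is at least one such patient?** The chance is 1 − (1 − *p*)^*n*, with *p* assumed. For *p* = 10% it is 47% with 6 dosed and 57% with 8. For *p* = 20% it is 74% and 83%.

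**3. PK timing and loss.** The last sample is due by 24 h 5 min, and 48 h − 24 h 5 min = 23.9 h. If the 48 h runs from the start of a 50-minute infusion, the margin is 48 h − 24 h 55 min = 23.1 h. Either way the profile is complete about a day before section 4.9 can exclude a late resection. Without added patients, each lost profile is 1/8 = 12.5% to 1/6 = 16.7% of the set. As a guide to precision, the 95% half-width of a mean in SD units is t(0.975, *n* − 1)/√*n*: 0.836 at *n* = 8, 0.925 at 7, 1.049 at 6 and 1.242 at 5. Losing one profile widens it by 10.6% (8 to 7) or 18.3% (6 to 5).

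**4. The population rules side by side.**

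| Dosed patient | Section 4.9 | Section 10.3.3 and study summary | Elsewhere |
|---|---|---|---|
| Resected after 48 h | Toxicity only | Had surgery, so included; out of tumour accumulation alone, if surgery timing counts as part of the treatment schedule | In OS and PFS (Table 5.2, footnote 4) |
| Never resected | Toxicity only | Read literally, in no analysis, safety included | In safety (6.2); in OS and PFS (Table 5.2, footnote 4) |

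**The case against.** The best defence is that section 4.9 is a general sentence about replacement, probably written with tissue in mind, and that the endpoint-specific text in section 10.3.2 governs feasibility by recording failures. This stands in part. A reader might infer that failed resections would be hidden; the documents do not support that, because a descriptive listing could show them. But section 10.3.2 gives no denominator, does not mention resection and does not override section 4.9, so the rate itself is unprotected.

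A reader might also infer that section 10.3.3 is simply the narrower rule. It is narrower only for late resection, and only if an incorrect treatment schedule is taken to cover surgery timing. The phrase is not defined, although sections 4.1 and 4.6 put the window in the treatment plan. For absent resection section 10.3.3 is no narrower, and read literally it conflicts with sections 4.9 and 6.2 on safety.

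Nor should a large loss of PK precision be inferred. A widening of about 52% (half-width 1.591 at *n* = 4 against 1.049 at *n* = 6) needs two of six profiles lost and nobody added, while section 4.9 allows additions. Section 10.3.2 plans curves and parameters, not confidence intervals for means.

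Finally, the feasibility intervals overlap heavily (4/4: 39.8-100%; 4/6: 22.3-95.7%), so the two rules would not support statistically different conclusions. That is correct; the difference lies in what the reported rate means.

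**Conclusion.** The point holds for feasibility and PK on the text as written. With 1 or 2 failures assumed among 6 to 8 dosed, no other failures and no top-ups, section 4.9 reports 100% where the all-dosed rate is 67-87.5%. Complete PK profiles can be discarded for a reason unrelated to PK. The conflict with section 10.3.3 is real but conditional for late resection; for absent resection the problem is that its surgery condition, taken literally, reaches safety.

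A reader might go further and call the OS, PFS and ORR analyses wrong. The documents support less: the OS and PFS population is unsettled between section 4.9, section 10.3.3 and footnote 4 to Table 5.2, and the ORR population needs stating. Section 4.2 itself warns that surgery may confound response.

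Severity is minor to should-fix: the affected endpoints are secondary or exploratory and descriptive, no decision threshold is stated, and section 6.2 keeps every dosed patient in primary safety.

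**What to change.** - **Section 4.9:** limit the exclusion to tumour bio-distribution and post-treatment tissue markers. Optional extra accrual for tissue endpoints can stay.
- **Sections 2.2.3, 6.3.3 and 10.3.2:** report feasibility step by step and as a composite. The composite denominator is all registered patients for whom product was to be prepared. Failures of production, delivery or administration stay in it, and withdrawals before dosing for other reasons are listed separately. An all-dosed denominator alone would miss failures that prevent dosing. For the resection step, use all dosed patients, count absent resection as a failure, and report resection outside the protocol's own 8-48 h window as its own category. Say in advance how that category enters the composite.
- **Section 10.3.2:** include every dosed patient with usable samples in PK.
- **Section 10.3.3 and the study summary:** apply the surgery condition to tissue endpoints only. Reconcile the OS and PFS population with footnote 4 to Table 5.2. State the ORR population, whichever the sponsor chooses.

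The cost is wording in these sections, with no new visits or data. The one downside is that the reported feasibility rate may be lower.
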